8.3. Targeted Number of Subjects and Justification

1) Number of Subjects to be Recruited

Taking into account the 20% withdrawal rate, this clinical study plans to enroll a total of 519 subjects (173 per group).

2) Calculation Basis

The primary objective of this study is to assess the efficacy of the study drug compared with placebo in preventing gallstone formation after gastrectomy in patients with gastric cancer. If the efficacy of DWJ1319 300 mg or 600 mg versus placebo is statistically significant, the study drug is considered to demonstrate its superiority. The endpoints are the proportion of subjects with gallstone formation within 12 months after gastrectomy. The hypothesis to test this is as follows:

$$H_0$$
 (null hypothesis): $P_{T1} = P_C$ and $P_{T2} = P_C$
 H_1 (alternate hypothesis): $P_{T1} \neq P_C$ or $P_{T2} \neq P_C$

P_{T1}: Proportion of subjects with gallstone formation after receiving 600 mg of DWJ1319

P_{T2}: Proportion of subjects with gallstone formation after receiving 300 mg of DWJ1319

Pc: Proportion of subjects with gallstone formation after receiving placebo

For testing of each treatment group versus the placebo, the significance level of the test is not corrected because a sequential multiple test (twice) is performed using the fixed sequential method. The test sequence is 600 mg of DWJ1319 versus placebo and 300 mg of DWJ1319 versus placebo.

The following results were referenced to calculate the number of subjects to be tested.

	Placebo	Ursodiol	Ursodiol	Ursodiol
	1 100000	300 mg	600 mg	1,200 mg
Study 1 ¹⁹⁾ (6M)	32.14% (18/56)	13.21% (7/53)	1.64% (1/61)	6.35% (4/63)
Study 2 ⁴⁾ (12M)	16.94% (112/661)	-	-	-
Study 3 ⁷⁾ (12M)	13.64% (6/44)	-	-	-

In this clinical study, the incidence of gallstones in placebo was estimated to be 18%, which is the weighted average of Studies 1, 2 and 3, where Study 1 is the result of placebo in obese patients who underwent gastrectomy and Studies 2 and 3 are the adjusted results of placebo in gastric cancer patients who underwent gastrectomy. Since it is difficult to estimate the incidence of gallstone of DWJ1319 by each dose, 7%, which is the weighted average of the three Ursodiol treatment groups in Study 1 was estimated as the rate of gallstone formation for the study drug.

In addition to the above assumptions, the significance level is 5% for two-sided test, 80% for test power, and the minimum number of subjects for 1:1:1 assignment is as follows:

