13.2. Early Termination of Study

Patients who have been confirmed for gallstone formation through the abdominal ultrasound during the post-randomization treatment period should stop participating in the study at the time of confirmation. The final assessment should be performed according to the schedule for visit 6/early termination. The subjects who are terminated early according to the early termination criteria are judged to have completed the study according to the study protocol instead of a dropout.

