14.2. General Principles of Result Analysis

All statistical analyses use SAS[®] 9.3 or higher and perform a two-sided test at a significance level of 5%.

The descriptive statistics (mean, standard deviation, minimum, median, and maximum) are provided for the continuous data (age, weight, height, BMI, etc.), and the frequency and proportion are provided for the categorical data (sex, etc.).

Confidential Page 33 of 51

If a missing value occurs due to a subject withdrawing before the end of the clinical study or a missing test at a certain point in time, etc., the analysis will be carried out without replacing the data unless otherwise specified and will be processed as missing (Observed Case).

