14.5.1. Adverse Events

Summary and analysis of adverse events are performed on treatment-emergent adverse events (TEAE). Adverse events following treatment are those that did not occur before the treatment, but the adverse events that occurred after the treatment or adverse events that became worse even if they are symptoms that existed prior to the treatment.

Descriptive statistics (number of subjects, incidence, and number of cases) will be presented by treatment group for the treatment emergent adverse event (TEAE), adverse drug reaction (ADR), and serious adverse event (SAE), and the two-sided 95% confidence interval for the incidence will also be presented. The differences in proportions between the treatment groups will be compared using the chi-square test or Fisher's exact test. All adverse events (TEAE) that occurred after the drug administration, adverse drug reactions (ADR) and serious adverse events (SAE) should be coded according to System Organ Class (SOC) and Preferred Term (PT) using MedDRA. The number of subjects who have manifested coded adverse events, incidence, number of cases, etc. should be presented for each treatment group. The relevance with the investigational product and severity will be assessed and presented by categorizing by SOC. In addition, a detailed report should be written about SAEs.

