15.2.3. Reporting of Adverse Events

Adverse events are those in which unexplained symptoms that appeared before the administration of the investigational product, either during the period of administration, or before the administration of the investigational product, and increased during the treatment period, regardless of the causality with the investigational product (including abnormal levels in clinical pathology), symptoms or illnesses, etc.

Adverse events should be monitored until the time of recovery to the status before treatment with the investigational product or the reference value, or until the investigator can determine that the adverse event has become normal or until further observation is deemed unnecessary. However, any new signs or symptoms that occur 30 days after the last administration of the investigational product will not be considered as adverse events.

Information on adverse events detected by the investigator during scheduled or unscheduled visits during the period of collection of adverse events should be recorded in the case record form, and the information to be collected is as follows:

- Name of adverse events (including the start date/date of disappearance, etc.)
- Assessment of severity (See Section 1 of 15.2.2)
- Causal relationship with the investigational product (See Section 2) of 15.2.2)
- Seriousness
- · Actions taken for investigational product
- · Measures made to treat the adverse event

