9.2.1 Overall Summary of Adverse Events

The number of subjects, expression rate (%) and the number occurrences of TEAEs and ADRs during the clinical study are presented as well as the 95% confidence intervals for the expression rate. However, a 95% accurate confidence interval for expression rate is presented when a cell with an expected frequency of less than 5 is equal to 20% or higher of all cells. The chi-square test or Fisher's exact test is used to determine whether there is a significant difference among the treatment groups, and the severity of the collected adverse events and their relevance to the investigational product are presented.

Also, serious adverse events, adverse events that resulted in permanent discontinuation of investigational product treatment, and adverse events that resulted in death are summarized.

A summary of the data is presented in the following tables.

- T. Overall Summary of TEAEs (Safety Set)
- T. Overall Summary of ADRs (Safety Set)

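### Adverse-event proportions are compared as if follow-up were equal, but exit at stone confirmation gives placebo a slightly shorter window; exposure-adjusted rates would be a cheap addition

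*Protocol*

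**What the plan says.** - **Exit rule.** Protocol section 13.2 says that a subject with a stone confirmed on ultrasound after randomisation "should stop participating in the study at the time of confirmation". The subject has the Visit 6/early termination assessments and counts as having completed, so the shorter follow-up does not appear as dropout.
- **End of adverse-event collection.** Section 15.2.3 says that "any new signs or symptoms that occur 30 days after the last administration of the investigational product will not be considered as adverse events". Events already present are followed to recovery or until further observation is judged unnecessary. Section 15.2.4 ties SAE notification to the treatment period. No other follow-up after a stone is planned.
- **Expected stone rates.** Section 8.3 plans for 18% on placebo. For active treatment it uses "7%, which is the weighted average of the three Ursodiol treatment groups in Study 1 was estimated as the rate of gallstone formation".
- **Comparison.** The safety set (14.1.2) is everyone treated. For TEAEs, ADRs and SAEs, section 14.5.1 gives numbers of subjects, incidence and numbers of cases, then: "The differences in proportions between the treatment groups will be compared using the chi-square test or Fisher's exact test". Section 14.5 has no person-time or time-to-event method.
- **Analysis-plan text in the same file.** SAP section 9.2.1 repeats the approach: "The chi-square test or Fisher's exact test is used to determine whether there is a significant difference among the treatment groups". SAP sections 6.5.1 and 9.1 derive days of exposure but only describe them by arm.

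**The concern.** A comparison of simple proportions is fair on exposure only if the arms are observed for about the same time. Here observation ends on the outcome that the drug is meant to prevent, so the design itself makes the windows unequal, in a known direction.

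Two things follow:

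- For adverse events in general, placebo subjects have less time to report one, so DWJ1319 would look slightly worse than placebo even if the true hazards were equal.
- For complications of the stones themselves, which section 5.2 gives as the reason for prevention, new events are no longer counted soon after the stone is found. That loss falls mainly on placebo.

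**Working it through.** **Inputs from the documents.** Stone rates of 18% and 7%, 173 per group (8.3); visits at months 3, 6, 9 and 12 (10.1); exit at confirmation (13.2); no new events counted from 30 days after the last dose (15.2.3); 10-20% of stones symptomatic (5.2).

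**Assumed, because the documents do not give it.** The timing of detection over the four visits; a constant adverse-event hazard, equal in all arms; other withdrawal ignored.

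**Planning figures reproduced.** The pooled source rates are (18+112+6)/(56+661+44) = 136/761 = 17.9% and (7+1+4)/(53+61+63) = 12/177 = 6.8%. The printed formula gives (1.96+0.842)² × (0.07×0.93 + 0.18×0.82)/0.11² = 138.01. Then 138/0.8 = 172.5, so 173 per group and 519 in total. The planning figures stand.

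**Who leaves early.** Expected stone formers are 173 × 0.18 = 31.1 on placebo and 173 × 0.07 = 12.1 per active arm. A stone found at month 12 costs no follow-up. With even timing, three quarters are found earlier: 0.75 × 18% = 13.5% against 0.75 × 7% = 5.25%, or about 23 against 9 of 173.

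**Mean window.** Mean = 12 − p × L, where L is the average number of months lost per stone former. For even timing, L = (9+6+3+0)/4 = 4.5.

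| Detection timing | L | Placebo | Active | Placebo shortfall |
|---|---|---|---|---|
| Even over four visits | 4.5 | 11.19 | 11.69 | 4.2% |
| 50/25/15/10% | 6.45 | 10.84 | 11.55 | 6.1% |
| All at month 3 | 9 | 10.38 | 11.37 | 8.7% |
| All at month 12 | 0 | 12 | 12 | none |

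The 30-day tail applies to completers as well, so it does not change the gap in months.

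**Effect on crude proportions.** For a 12-month risk R, let h = −ln(1−R)/12. The expected crude proportion is (1−p)R + p × Σ w(1−exp(−h×t)), with w the share of stones found at visit t.

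| R | Even: placebo vs active (ratio) | All at month 3: placebo vs active (ratio) |
|---|---|---|
| 5% | 4.67% vs 4.87% (1.044) | 4.33% vs 4.74% (1.095) |
| 30% | 28.1% vs 29.3% (1.041) | 26.1% vs 28.5% (1.090) |
| 50% | 47.1% vs 48.9% (1.038) | 43.9% vs 47.6% (1.085) |
| 80% | 76.3% vs 78.6% (1.029) | 71.6% vs 76.7% (1.072) |

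For one active arm against placebo at 173 each, a nominal 5% test rejects in 5.1% to 7.9% of trials over these risks with even timing. In the month-3 extreme it rejects in 5.4% to 19.5%.

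**Stone-related events.** After a stone at month 3, 6 or 9, the 30-day tail covers about 1 of 9, 1 of 6 or 1 of 3 remaining months. The share unobserved for new events is 8/9 = 89%, 5/6 = 83% or 2/3 = 67%. Applying 10-20% to all expected stone formers gives 31.1 × 0.10 to 0.20 = 3 to 6 placebo subjects and 12.1 × 0.10 to 0.20 = 1 to 2 per active arm. This includes stones found at month 12 and symptoms at any time, so it is an upper guide.

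**The case against.** The strongest reply is that the effect is small and cannot hide harm from the drug. No confirmatory safety hypothesis is set, the bias for general events runs against the sponsor's product, stones themselves are the primary endpoint, and exposure by arm is tabulated under SAP 9.1, so a reader can see the imbalance. All of this stands and limits the weight of the point. It does not make the stated test account for unequal windows.

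The reply also rightly blocks three stronger readings that a reader might infer:

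- **That 18% and 7% leave early.** These are 12-month rates, and stones found at the last visit cost nothing. They are also planning rates for an externally assessed endpoint (14.4.1), while exit follows the ultrasound finding at the site (13.2), so actual exits may differ.
- **That the general bias can exceed 10%.** The between-arm ratio stays below 1.10 even in the month-3 extreme.
- **That most biliary harm after a stone goes unseen.** The 67% to 89% are shares of time, not of harm. The documents give no timing of complications, new events within the 30-day tail still count, and events present at exit are followed up.

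A further fair objection is that person-time rates should not replace the proportions. Treatment starts soon after surgery. If hazards are higher early, stone formers contribute mainly high-hazard time, and a rate would overstate harm on placebo.

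**Conclusion.** The point holds as a cheap improvement. The planned comparison treats unequal adverse-event windows as equal, and placebo has the shorter window whenever some stones are found before month 12.

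At the planned rates with even detection, the gap is about half a month (4.2%) and the spurious risk ratio about 1.03 to 1.04. The range runs from no effect to just under 1.10, depending wholly on detection timing, which is assumed. The figures also rest on constant, equal hazards and on exits at the site matching the planned stone rates.

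The gap in stone-related follow-up is large as a share of time but concerns few subjects. It should be disclosed rather than read as a demonstrated loss of most biliary harm.

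**What to change.** Leave the exit rule as it is. In Protocol section 14.5.1, and correspondingly in SAP 9.2.1:

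1. Keep the crude proportions and their tests.
2. For TEAEs, ADRs and SAEs, add exposure-adjusted first-event rates: subjects with an event per person-year, counted from first dose to the earlier of the first event or the end of the adverse-event window, with rate ratio and 95% CI. Alternatively, add a time-to-first-event comparison censored at the end of that window.
3. Base any between-arm safety statement on these results alongside the crude percentages.
4. State that new biliary complications after stone confirmation are not captured beyond the 30-day window. Neither added analysis recovers them.

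The cost is a sentence or two of text and a few tables from dates already recorded. The rate ratio assumes a roughly constant hazard; the time-to-first-event version avoids that assumption. Follow-up to month 12 after exit would be optional extra work and is not part of this point.

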14.5.2. Laboratory Tests and Vital Signs

Descriptive statistics (mean, standard deviation, minimum, median, and maximum) will be presented by treatment group for the measurements at each time point and the change from baseline after the administration of the investigational product, and the frequency and proportion will be presented for categorical measurement results.

The treatment groups will be compared by ANOVA or a Kruskal–Wallis test for continuous data, and by the chi-square test or Fisher's exact test for categorical data.

For laboratory tests, classification should be made into a normal or not clinically significant abnormality and clinically significant abnormality. A shift table will be presented for changes in the post-administration compared to pre-administration of the investigational product. The chi-square test or the Fisher's exact test will be used to analyze the proportion of patients who have changed to clinically significant abnormalities post-dose at a not clinically significant abnormality.

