8.1. Inclusion Criteria

- 1) Patients who voluntarily agree to participate in the study and sign the informed consent form
- 2) Patients at least 19 years of age at the time of informed consent
- 3) Patients who were diagnosed with gastric cancer and underwent any one of the following gastrectomies
 - Total gastrectomy
 - Distal gastrectomy
 - Proximal gastrectomy
- 4) Patients who underwent D1+ or D2 lymph node dissection
- 5) Patients with ECOG performance status scale ≤ 1 point (Appendix 1)
- 6) Life expectancy of at least 3 months
- 7) Patients who can be enrolled in the study within 2 weeks from gastrectomy

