10.1. Study Design

This is a multicenter, randomized, double-blinded, placebo-controlled, phase 3 study. Subjects are patients who have been diagnosed with gastric cancer and underwent gastrectomy for treatment. Screening will be conducted on subjects who gave an informed consent to participate in the study. Subjects who meet the inclusion criteria and do not qualify as exclusion criteria will be randomly assigned to DWJ1319 300 mg (DWJ1319 300 mg, once a day), DWJ1319 600 mg (DWJ1319 300 mg, twice a day), or placebo (1: 1: 1). For randomization, stratified randomization using the study site, the lymph node resection range (D1+, D2), and the type of gastrectomy as the stratification factors will be performed and randomization will be performed within 2 weeks from gastrectomy. During the study period, the subjects will visit the study site at screening, randomization (Day 1) and at 3-month interval after the administration of investigational product (at 3, 6, 9, and 12 months) to undergo protocol-specified tests and procedures at each visit. However, any subject with formation of gallstone confirmed during the treatment period will terminate the study at the time of confirmation.

Visit 1	Visit 2	Visit 3	Visit 4	Visit 5	Visit 6
Until Week -2	Day 1	Month 3 ± 1 Week	Month 6 ± 1 Week	Month 9 ± 1 Week	Month 12 ± 1 Week
Screening	Randomizatio n	Treatment period			

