11.2.10. Laboratory Tests

Laboratory tests are carried out using the Central lab and are performed in a fasted state at Visits 1, 4 and 6 or at the time of early termination/withdrawal. If screening results do not meet the inclusion/exclusion criteria, they may be retested only once. Women of childbearing age should be checked for pregnancy through a urine hCG test at Visit 1. In addition, if it is deemed necessary based on the investigator's judgment, additional tests may be conducted.

Laboratory test items are as follows:

Hematology	WBC, RBC, Hemoglobin (Hb), Hematocrit (Hct), Platelet count, WBC differential count
	(Neutrophil, Lymphocyte, Monocyte, Eosinophils, Basophils)

Confidential Page 27 of 51

Biochemical test	Glucose, Total protein, Albumin, Total cholesterol, Triglyceride, Total bilirubin, alanine transaminase (ALT), aspartate transaminase (AST), alkaline phosphatase (ALP), blood urea nitrogen (BUN), gamma-glutamyl transferase (γ-GTP), Uric acid, Creatinine, sodium, potassium, chloride, calcium, HbA1c*, eGFR
Urinalysis	Bilirubin, urobilinogen, Blood, Glucose, pH, Protein, Specific Gravity
Pregnancy test**	Urine HCG

[†] HbA1c: It will be performed once at screening, and if there is a test result within the last 3 months, it can be replaced with the screening test result.

In addition, only the liver function tests (ALT, AST, ALP, y-GTP and total bilirubin) among the biochemical tests are performed at Visits 3 and 5.

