14.5. Safety Analysis

Safety analysis is performed for the safety analysis set. Safety endpoints are adverse events, laboratory tests, vital signs, and physical examinations. The baseline for each safety endpoint should use the results of the last assessment performed prior to the first dose of the investigational product.

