9.2.4 Evaluation of Each Laboratory Parameter

For the continuous variables of the clinical laboratory test categories, descriptive statistics (number of subjects, mean, standard deviation, median, minimum, and maximum values) are presented for each treatment group with respect to the measured value and the change relative to the baseline at each visit. For intra-group changes relative to the baseline, paired t-test or Wilcoxon signed rank test is performed for comparison according to the result of the normality test. For the differences among the treatment groups, ANOVA or Kruskal-Wallis test is performed for comparison according to the result of the normality test.

A summary of the data is presented in the following tables.

- T. Summary of Hematology Data [Parameter] (Safety Set)
- T. Summary of Serum Chemistry Data [Parameter] (Safety Set)
- T. Summary of Urinalysis Data [Parameter] (Safety Set)

In order to confirm any changes in normality status after the administration of the investigational product compared to the baseline, data is divided into the normal, abnormal NCS and abnormal CS categories and summarized in shift table form by treatment group at each evaluation point. The McNemar's test is used for intra-group changes and the chi-square test or the Fisher's exact test is used to compare differences among the treatment groups. In addition, a list is presented of subjects who were normal or abnormal NCS at baseline but showed abnormal CS changes after administration of the investigational product.

A summary of the data is presented in the following table and list.

- T. Shift from Baseline at Post-Baseline on Hematology Data [Parameter] (Safety Set)
- T. Shift from Baseline at Post-Baseline on Serum Chemistry Data [Parameter] (Safety Set)
- T. Shift from Baseline at Post-Baseline on Urinalysis Data [Parameter] (Safety Set)
- L. Subjects Shifting from Normal or NCS at Baseline to CS at Post-Treatment on Laboratory (Safety Set)

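### Continuous laboratory and vital-sign data are compared across arms with no baseline term and no planned dose-minus-placebo difference with confidence interval: a valid test, but a minor, avoidable loss of precision and estimation

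*Protocol*

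**What the plan says.** Protocol 14.5.2 has descriptive statistics "presented by treatment group for the measurements at each time point and the change from baseline after the administration of the investigational product". It then gives the between-arm test: "The treatment groups will be compared by ANOVA or a Kruskal–Wallis test for continuous data". It does not say whether that test is applied to the measurement, to the change, or to both.

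SAP 9.2.4 adds how the test is chosen: "For the differences among the treatment groups, ANOVA or Kruskal-Wallis test is performed for comparison according to the result of the normality test". SAP 9.3.1 does the same for vital signs. The ANOVA code in SAP 15.3 models the variable on treatment alone.

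On baseline, Protocol 14.5 says: "The baseline for each safety endpoint should use the results of the last assessment performed prior to the first dose of the investigational product". Protocol 10.1 says that "randomization will be performed within 2 weeks from gastrectomy", and Protocol 11.2.10 schedules the full laboratory panel: "Laboratory tests are carried out using the Central lab and are performed in a fasted state at Visits 1, 4 and 6". Liver function tests are added at Visits 3 and 5. The laboratory baseline is therefore normally the Visit 1 value, taken close to surgery, and it is compared with values at Months 3 to 12.

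The plan also has shift tables and a between-arm test of shifts to clinically significant abnormality (Protocol 14.5.2). Clinically significant AST and ALT abnormality at 6 and 12 months has its own logistic comparison of each dose with placebo (Protocol 14.4.3, SAP 8.4.3).

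**The concern.** Two things are left on the table.

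The first is precision. A one-way test on the raw value ignores baseline, and a one-way test on the change subtracts it with a fixed coefficient of one. Neither uses the coefficient that the data support. With a baseline taken around gastrectomy, the correlation with later values could be weak for some analytes. Subtracting baseline then adds noise. For measures that stay stable within a subject the correlation could be strong, and ignoring baseline is then wasteful. The plan does not say which scale is tested, so the reader cannot tell which loss applies.

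The second is estimation. A three-arm omnibus p-value answers whether the arms differ somewhere. A safety reader wants to know how far each dose moves ALT or bilirubin relative to placebo, and what size of shift the data exclude. No such difference with a confidence interval is planned for the continuous values.

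**Working it through.** **Plan's own figure.** The documents give no precision or power figure for these comparisons. The only calculated figure is the sample size for gallstone rates. It reproduces: (1.96 + 0.842)² × {0.07 × 0.93 + 0.18 × 0.82} / 0.11² = 138.01, stated as 138 per group. It does not bear on this point, except that 138 serves below as an illustrative group size.

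**Inputs.**
- Test: one-way, no covariate (Protocol 14.5.2; SAP 9.2.4, 9.3.1, 15.3).
- Tested scale: not stated, so both are worked.
- Correlation r between baseline and follow-up: not in the documents; assumed 0.2, 0.5 and 0.8.
- Ratio of baseline SD to follow-up SD: not in the documents; assumed equal to 1.

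**Formulas.** Set the follow-up variance to 1.
- Raw value: variance 1.
- Change from baseline: 1 + 1 − 2r = 2(1 − r).
- ANCOVA on baseline: residual variance 1 − r².

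The standard-error ratios to ANCOVA are:
- change: √[2(1 − r)/(1 − r²)] = √[2/(1 + r)]
- raw: 1/√(1 − r²)

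| r | Change variance | ANCOVA variance | SE ratio, change | SE ratio, raw |
|---|---|---|---|---|
| 0.2 | 1.60 | 0.96 | √1.667 = 1.29 | 1/√0.96 = 1.02 |
| 0.5 | 1.00 | 0.75 | √1.333 = 1.15 | 1/√0.75 = 1.15 |
| 0.8 | 0.40 | 0.36 | √1.111 = 1.05 | 1/√0.36 = 1.67 |

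The two unadjusted analyses cross at r = 0.5. Below it the change is the worse choice; above it the raw value is. Apart from a negligible loss of degrees of freedom, ANCOVA is at least as precise as either, so it also removes the dependence on the unstated scale.

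**Validity and power.** A simulation used three arms of 138, equal variances, 4,000 runs per setting, and the unadjusted tests applied to the change. With no treatment effect, rejection rates were between 4.5% and 5.3% for ANOVA, Kruskal-Wallis and ANCOVA. With an assumed shift of 0.3 follow-up SD in one arm, the power of the omnibus test was:

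| r | ANOVA | Kruskal-Wallis | ANCOVA |
|---|---|---|---|
| 0.3 | 58% | 56% | 78% |
| 0.5 | 73% | 71% | 85% |
| 0.7 | 93% | 91% | 96% |

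**Sensitivity to the SD ratio.** With a baseline SD k times the follow-up SD, the change variance is 1 + k² − 2rk. At k = 0.7 (assumed) the change-to-ANCOVA ratios fall to √(1.21/0.96) = 1.12, √(0.79/0.75) = 1.03 and √(0.37/0.36) = 1.01. The raw-value ratios do not depend on k.

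**The case against.** The strongest reply is that nothing here is wrong. Randomisation makes the one-way tests valid, the comparisons are unpowered safety summaries, and they play no part in the fixed-sequence test of the primary endpoint. That stands, and it sets the severity.

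The size of the loss is also uncertain. If correlations are weak because baseline is peri-operative, and the raw value is what is tested, the loss is only 2% in the standard error at r = 0.2. That too stands, and it is why both scales must be shown.

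Three stronger readings are tempting and should be resisted.

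- A reader might infer that peri-operative baselines are more variable than later values, which would enlarge the loss on the change scale. The documents do not support this. Exclusion criterion 11 removes subjects with screening ALT, AST, BUN or total bilirubin above 2.5 times the upper limit of normal. That truncates baseline but not follow-up for those analytes, and so points the other way.
- A reader might infer that the plan yields no effect estimate at all. It reports the mean and SD of the value and of the change by arm and visit, so a crude difference can be derived. What is missing is a planned difference of each dose from placebo with its interval.
- A reader might infer that liver safety is left to these tests. It is not. AST and ALT abnormality has a per-dose logistic comparison, with odds ratios and 95% CIs in SAP 8.4.3. There are also shift tables, and clinically significant laboratory changes are recorded as adverse events (Protocol 15.1). Appendix 3 describes liver enzyme elevations as rare, and rare individual elevations are found by those analyses more than by a sharper comparison of means.

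The choice of test by a normality result appears only in the SAP, and no harm from it has been shown. It is not a separate defect here.

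**Conclusion.** The point holds as a minor one. The plan fixes a between-arm test that does not adjust for a baseline value the trial already collects, and it plans no dose-minus-placebo difference with confidence interval for continuous laboratory and vital-sign data. The standard error exceeds that of baseline-adjusted ANCOVA by about 5% to 29% if the change is tested, and by about 2% to 67% if the raw value is tested.

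These ranges rest on assumed correlations of 0.2 to 0.8 and equal variances; the documents supply neither, nor the tested scale. The finding is lost precision and missing estimation. It is not bias, not inflation of type I error, and not a threat to the primary conclusion.

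**What to change.** In Protocol 14.5.2 and SAP 9.2.4 and 9.3.1, replace the between-arm ANOVA or Kruskal-Wallis test of continuous values by ANCOVA of the post-dose value at each visit. The covariates are the baseline value, lymph node resection range and type of gastrectomy. Use the log scale for skewed analytes (AST, ALT, ALP, γ-GTP, bilirubin, triglyceride). Report 600 mg minus placebo and 300 mg minus placebo, or geometric mean ratios, with 95% CIs. Stating the post-dose value as the outcome also settles the tested scale, and the normality-test choice between the two tests is no longer needed for this comparison.

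Keep the descriptive statistics for change, the shift tables and the AST/ALT abnormality analysis as they are.

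The cost is wording plus a small code change. SAP 15.3 already has an ANCOVA template with least-squares means and confidence limits. The baseline value has to be added as a continuous term and the contrast written for each dose. No new data are needed.
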